7.10 Healthcare Resource Utilization Analysis (Part 3 only)

Healthcare resource utilization data will be summarized in descriptive statistics of medical encounters in the full analysis set. Specifically, the number of hospitalizations, number of intensive care unit (ICU) stays, number of emergency room stays, number of outpatient visits, length of hospital stay, length of stay in ICU, length of stay in hospital floor bed. Visit reasons for each of these and primary diagnosis at discharge will be summarized over time.

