5.4.3.2 Part 3 Secondary Endpoints

- ORR by investigator assessment.
- DOR.
- CBR (response of sCR, CR, VGPR, PR, or minimal response) by IRC and investigator assessment.
- Duration of clinical benefit.
- DCR (CBR + stable disease [SD]) by IRC and investigator assessment.
- Duration of disease control.
- PFS (time from the date of first dose until the sooner of the date of PD, defined by IMWG criteria [(Appendix F)] or the date of death due to any cause by IRC and investigator assessment.
- TTP by IRC and investigator assessment.
- OS (date from first dose to the date of death due to any cause).
- Rate of MRD negative status at a sensitivity of 10⁻⁵ in patients achieving CR.
- Duration of MRD negativity at a sensitivity of 10⁻⁵ in patients achieving CR.
- AEs, SAEs, laboratory assessments, supportive care use.
- Eastern Cooperative Oncology Group (ECOG) status.
- ADA incidence and characteristics (eg, titer and specificity) and NAb.
- Length of hospital stay, types of hospital stay, and other healthcare resource utilization data as defined in Section 9.3.13.
- No worsening of disease symptoms (includes bone aches or pain, back pain, hip pain, arm or shoulder pain, chest pain, and pain increasing with activity) from baseline at 12 weeks across doses of modakafusp alfa as measured by the patient-reported outcome (PRO) instrument European Organisation for Research and Treatment of Cancer QLQ Questionnaire Multiple Myeloma Module (EORTC QLQ-MY20).
- Summary statistics by dose level and cycle day for the following PK parameters in Chinese patients with intensive PK schedule: C_{max} , AUC_{∞} , AUC_{last} , λ_z , t_{max} , CL, V_{ss} , and $t_{1/2z}$.

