6.3.1 Duration of an Individual Patient's Study Participation

Patients may receive modakafusp alfa until they experience PD, unacceptable toxicity, or any other discontinuation criterion is met (Section 9.4). In Parts 1 and 2, the maximum scheduled duration of treatment will be 1 year; however, patients with clinical benefit can continue treatment beyond 1 year with explicit sponsor approval. Patients in the modakafusp alfa plus dexamethasone cohort can continue receiving single-agent modakafusp alfa if the investigator considers that there are clinical reasons (for example safety) supporting the removal of dexamethasone from the treatment.

Patients may be treated in Part 3 until progression or other discontinuation criteria are met. If the investigator considers that treatment after PD is in the patient's best interest, it can be approved after consultation with the sponsor.

Patients will be evaluated 30 days (EOT visit) after the last dose of modakafusp alfa or right before the start of subsequent systemic anticancer therapy to permit the detection of any delayed TEAEs.

Patient participation includes up to 21 days of screening, 1 year of treatment (Parts 1 and 2) or until disease progression (Part 3), and 1 month posttreatment follow-up (EOT visit). Patients who discontinue for reasons other than PD will continue PFS follow-up every 4 weeks from the EOT visit until the occurrence of PD, death, the start of subsequent systemic antineoplastic therapy, study termination (Section 9.4), or until 6 months after the discontinuation of study treatment, whichever occurs first. OS follow-up continues every 12 weeks from the EOT visit until death, study termination, or patient withdrawal.

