9.3.13 Healthcare Resource Utilization

Healthcare resource utilization, including hospitalizations and outpatient visits, will be evaluated as a secondary endpoint. Healthcare resource utilization, including information related to hospitalization or outpatient clinics, will be collected from all patients, regardless of the reason for the medical care encounter on Day 1 of each cycle and at EOT per the SOE (Appendix A).

Examples of data to be collected include the length of hospital stay, types of hospital stay (eg, intensive care unit), types of outpatient visits (eg, emergency room visit), and reasons for hospitalization and outpatient visits.

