- All PROs should be administered D8 of each cycle, except for C1 when the EORTC QLQ-MY20 should be administered on D1 and D8 (ie, C1D1 and C1D8) and the EQ-5D-5L on D1 (ie, C1D1). On C1D1, PROs may be completed within a +1-day window, and on the rest of the days PROs may be completed within a 2-day window. On days when PROs are administered during clinic visits, the EORTC QLQ-MY20 and EQ-5D-5L should be administered to patients when they arrive for their scheduled visits, before any clinical measurements, assessments, evaluations, or procedures being performed (see Section 9.3.12). On days when PROs are not completed at the clinic (ie, Day 8 of each cycle starting with Cycle 3), site staff should remind each patient at every cycle to complete their PROs. Healthcare utilization data is collected on D1 of every cycle, starting at C1, and at EOT.
- Immediately following the bone marrow aspiration/biopsy obtained for local disease assessment at screening and for confirmation of a suspected CR, BMA will be collected for evaluation of minimal residual disease and sent to a central laboratory for analysis. If a BMA/biopsy drawn before consent, within 5 weeks of first dose, is used for local disease assessment at screening, the first BMA pull will be drawn for the MRD sample. Additionally, BMAs will be requested for MRD assessment every 6 months after suspected CR to further characterize MRD status. Screening MRD samples will be obtained in China based on acceptability of method chosen.
- Following the collection of BMA for MRD sample at screening, an additional 3 mL pull of BMA will be collected for cytogenetic analysis and central evaluation of both tumor and immune fractions of bone marrow.
- hh. Sample collection not applicable to patients enrolled in China. See Sections 9.3.11.3.2.6, 9.3.11.3.2.7 and 9.3.11.4.
- Cytogenetic results from samples taken within 5 weeks prior to first dose are acceptable for stratification. If a previous result is not available and the patient is known to have high-risk disease [ie, del17, t(4;14) and/or t(14;16)] from prior cytogenetic testing, regardless of timing, they should be stratified as high risk for the purpose of enrollment. Additionally, all patients should have a sample from screening sent for central cytogenetic analysis ("BMA for cytogenetics").
- ji. A portion of this sample will be used for exploratory analyses.

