Appendix J Protocol History Including EUCTR Consolidation Table

Protocol History: Amendments Harmonized with Global Protocol Amendment 9

Date	Amendment Number	Region
26 February 2024	Amendment 10 v1 (not implemented)	Global
02 August 2023	Amendment 9	Global
10 February 2023	Amendment 8 CH v1	Local China
12 July 2022	Amendment 8 NO v1	Local Norway
23 June 2022	Amendment 8 GB v1	Local United Kingdom
01 March 2022	Amendment 8	Global
25 October 2021	Amendment 7 (not implemented)	Global
16 October 2020	Amendment 6	Global
03 July 2019	Amendment 5	Global
22 October 2018	Amendment 4	Global
29 June 2018	Amendment 3	Global
07 November 2017	Amendment 2	Global
05 April 2017	Amendment 1	Global
14 December 2016	Initial protocol	Global

Protocol History: Amendments Not Harmonized with Global Protocol Amendment 9

Country	Date of Amendment	Amendment Title
France	15 July 2022	Amendment 8 FR v1
France	12 August 2022	Amendment 8 FR v2
Germany	25 August 2022	Amendment 8 DE v1
Czech Republic	04 November 2022	Amendment 8 CZ v1
Japan	31 March 2022	Amendment JP v1
Japan	12 August 2022	Amendment JP v2
Japan	20 October 2022	Amendment JP v3

Country Specific Requirements/Differences for the European Union

(Consolidation of country-specific protocol differences approved in different member states under the Directive 2001/20/EC that will transition to the Regulation [EU] No. 536/2014)

	Summary of Changes			
Country	Section Number	Country Specific Language	Country Specific Language in Tracked Changes against Global Protocol Language	
France v2	8.1 Study Drug Administration Section 8.6.1 Premedications	hospitalization is required for the first [infusion] of modakafusp alfa.	Modakafusp alfa doses of 120 and 240 mg will be administered over 1 hour (±10 minutes). Hospitalization is required for Cycle 1 Day 1 dose administration of modakafusp alfa.	
France v1	7.2 Exclusion Criteria #12	urine or or serum	Female patients who are lactating and breastfeeding or have a positive urine or serum pregnancy test during the screening period or a positive urine or serum pregnancy test on Day 1 before first dose of study drug if applicable.	

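### Healthcare utilization is summarised as raw encounter counts over an on-treatment window that can differ by dose; a rate per patient-month should be added

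*SAP*

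**What the plan says.** Protocol 5.4.3.2 lists the endpoint among the Part 3 secondary endpoints: "Length of hospital stay, types of hospital stay, and other healthcare resource utilization data as defined in Section 9.3.13". Protocol 9.3.13 says that the information "will be collected from all patients, regardless of the reason for the medical care encounter on Day 1 of each cycle and at EOT". The footnote to the Part 3 schedule in Appendix A agrees: "Healthcare utilization data is collected on D1 of every cycle, starting at C1, and at EOT". That schedule has no utilization collection in PFS or OS follow-up.

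The length of the window comes from Protocol 6.3.1: "Patients may be treated in Part 3 until progression or other discontinuation criteria are met", and "Patients will be evaluated 30 days (EOT visit) after the last dose of modakafusp alfa", or just before new systemic therapy starts.

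SAP 7.10 gives descriptive statistics in the full analysis set: "the number of hospitalizations, number of intensive care unit (ICU) stays, number of emergency room stays, number of outpatient visits, length of hospital stay", with length of stay in the ICU and on a hospital floor bed. It adds that visit reasons and discharge diagnoses are summarised over time. It states no rate, person-time or fixed window, and no rule for encounters that the protocol itself requires. One such encounter is in the France-specific text in Protocol Appendix J: "Hospitalization is required for Cycle 1 Day 1 dose administration of modakafusp alfa".

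**The concern.** A count is interpretable only with the time over which it was collected. Here that time is the patient's time on treatment plus about 30 days. It ends with progression, toxicity or another reason for stopping, and the two doses may affect each of these. A dose that keeps patients on treatment longer gives them more time in which an admission or visit can be recorded.

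Part 3 exists to identify the better dose from the totality of data in both arms. An unadjusted utilization table could then count against the dose with longer treatment merely because its patients were watched for longer. SAP 7.9 deals with the same problem for the questionnaires, where patients are expected to have a score only in cycles in which they were dosed. SAP 7.10 has no equivalent.

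**Working it through.** The documents state no utilization rate, expected duration or precision for this endpoint, so there is no planned figure to reproduce. The following illustrates the mechanism.

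**Inputs from the documents**
- 118 patients per arm (Protocol 6.2).
- 28-day cycles with one infusion on Day 1 (Q4W schedule).
- EOT visit 30 days after the last dose (Protocol 6.3.1).
- 30.4375 days per month, the conversion in SAP 7.8.1.

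**Assumptions**
- The true rate is equal in both arms: 0.05, 0.10 or 0.20 hospitalizations per patient-month.
- All patients in an arm receive the same number of cycles, without delays: 3 vs 4, 3 vs 6, 4 vs 8 or 6 vs 8.

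**Formulas**
- Window in months = [28 × (cycles − 1) + 30] / 30.4375
- Expected count per arm = 118 × rate × window

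**Windows**
- 3 cycles: 86 / 30.4375 = 2.83 months
- 4 cycles: 114 / 30.4375 = 3.75 months
- 6 cycles: 170 / 30.4375 = 5.59 months
- 8 cycles: 226 / 30.4375 = 7.43 months

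**Expected hospitalizations per arm at 0.10 per patient-month**

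| Cycles, shorter vs longer arm | Counts | Raw-count ratio | Ratio per patient-month |
|---|---|---|---|
| 3 vs 4 | 33.3 vs 44.2 | 1.33 | 1.00 |
| 3 vs 6 | 33.3 vs 65.9 | 1.98 | 1.00 |
| 4 vs 8 | 44.2 vs 87.6 | 1.98 | 1.00 |
| 6 vs 8 | 65.9 vs 87.6 | 1.33 | 1.00 |

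At 0.05 the counts halve and at 0.20 they double. The ratios do not change, because they depend only on the windows (for example 170 / 86 = 1.98).

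**Total days and length per stay.** Total hospital days per patient scale with the window in the same way as the counts. Mean length per stay does not, since lengthening the window adds stays without lengthening each one.

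**Scheduled visits, only if they are recorded as outpatient visits.** The Part 3 schedule has 5 visits in each of Cycles 1 and 2, 1 in each later cycle, an extra Day 2 visit in Cycles 5 and 11, and EOT. This gives 12 visits for 3 cycles, 13 for 4, 16 for 6 and 18 for 8. If recorded, they would add 12 to 18 visits per patient, with ratios between the longer and shorter arm of 1.08 (13/12) to 1.38 (18/13) in the four scenarios.

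**The case against.** The strongest reply is that little depends on this table. The endpoint is descriptive, the protocol plans no formal comparison of the arms, and SAP 7.10 does not itself say that the summary is by dose. SAP 7.7 reports treatment duration and number of cycles in the same analysis set, so a reader could set counts beside exposure. This limits the consequence but does not remove the defect. A separate exposure table leaves the adjustment to the reader, and pooled counts would still lack a time denominator.

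It is also fair to say that more use in the longer-treated arm is a tendency and not a certainty. Encounters concentrated in early cycles, or a lower rate in that arm, could cancel or reverse it.

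A reader might infer four stronger points that the documents do not support:
- **Scheduled study visits are certainly counted as outpatient visits.** Protocol 9.3.13 speaks of medical care encounters and gives an emergency room visit as its example. The eCRF instructions are not in the documents, so this is possible but not shown.
- **Counts will fall artificially from Cycles 1 and 2 onward.** SAP 7.10 summarises reasons and discharge diagnoses over time. It does not say that the counts are tabulated by cycle.
- **The French Cycle 1 admission biases the comparison.** The requirement makes no distinction by dose and patients are randomised 1:1, so it mainly raises the level in both arms. The share of French patients is not given.
- **The endpoint is invalid because it includes all causes.** All-cause capture is the stated design and suits an objective of assessing utilization.

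**Conclusion.** The concern holds for the counts and for total hospital days. The plan reports them without a time denominator over a window that follows time on treatment. At an equal true rate, a difference of 3 vs 4 up to 3 vs 6 cycles produces a raw-count ratio of 1.33 to 1.98 where the ratio per patient-month is 1.00. The size rests on the assumed durations and on equal, constant rates, because the documents give neither. Average length per stay is not affected in the same way.

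The reach is limited to a descriptive secondary endpoint. The primary ORR analysis, the futility boundaries and the safety stopping rules are untouched. The change is worth making because it is cheap and because the two doses' figures will be read side by side.

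**What to change.** In SAP 7.10, keep the planned all-cause counts and add:
1. For each encounter type, the rate per patient-month from first dose to EOT, by dose level, with the person-time shown.
2. Total hospital days per patient-month over the same window.
3. If any summary of counts by cycle is produced, the patients still under observation in that cycle as its denominator.
4. Using the recorded reason, a separate line for protocol-required admissions (the French Cycle 1 Day 1 stay). Do the same for scheduled study visits only if the eCRF records them as outpatient visits.

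The cost is a few sentences in the SAP and a few lines of programming. The overall rates need only the encounter counts and the first-dose and EOT dates. Protocol 9.3.13 lists reasons among the data collected, so the separate lines need no new field if the recorded reason identifies a protocol-required encounter. It does not explicitly list encounter dates, so availability should be confirmed before a by-cycle table is promised. No additional patients or visits are required.

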7.11 Pharmacokinetic/Pharmacodynamic Analysis

7.11.1 Pharmacokinetic Analysis

7.11.1.1 Serum Modakafusp alfa Concentrations

Blood samples will be collected at prespecified time points as described in the study protocol for the measurement of serum modakafusp alfa concentrations. Individual serum concentration data will be listed by patient, dosing schedule (A, B, C, and D), dose level, study day, and sampling time. Both nominal (scheduled) and actual sampling times will be presented in the listings.

Serum modakafusp alfa concentrations will be summarized by nominal time post dose, grouped by dosing schedule, dose level, nominal infusion duration, and study day by phases (escalation and expansion). Summary statistics will be reported at nominal sampling times; means will be reported if the number of observations above the lower limit of quantitation (NALQ) is $\geq 50\%$ of the number of patients. The summary statistics will consist of: N, NALQ, arithmetic mean, standard deviation (SD), coefficient of variation (CV), geometric mean, geometric CV, median, min, and max. The SD and CV will be reported on at least 3 non-missing values. Modakafusp alfa concentrations that are below the limit of quantitation (BLQ) will be set to zero for calculation of summary statistics, except for geometric means, where BLQ values will be considered missing.

Concentration data that are considered anomalous may be excluded from the concentration summaries and plots. Evidence or explanations will be provided in the clinical study report to justify the exclusion of concentration data.

Mean and individual modakafusp alfa serum concentration data will be plotted over nominal sampling time, grouped by dosing schedule, dose level, nominal infusion duration, and study day on both linear and semi-logarithmic scales. Mean and individual serum concentrations will be plotted over time (labeled with cycle number), grouped by dosing schedule and dose level on a linear scale by phases (escalation and expansion). Visual inspection of the serum concentration-time plots will be used to make inferences regarding the attainment of PK steady-state by cycle.

BLQ values will be plotted as zero on a linear scale and treated as missing on a semi-logarithmic scale.

7.11.1.2 Serum PK Parameters

The serum PK concentration-time course data will be used to calculate standard PK parameters using noncompartmental methods with Phoenix WinNonlin.

Actual sampling times will be used for the calculation of PK parameters. In the event that actual collection times are either unreliable or missing, nominal collection times will be used. For the calculation of PK parameters, serum concentrations of modakafusp alfa that are BLQ will be treated as zero prior to t_{max} , missing between t_{max} and the time of the last measurable concentration, and the concentration-time curve will be considered to have terminated at the time of the last measurable concentration. If measurable concentrations are near the lower limit of quantification (LLOQ) or imbedded between BLQ concentrations, these values may be excluded at the discretion of the Clinical Pharmacologist. Concentration data that are considered anomalous may not be used in the calculation of PK parameters; evidence or explanations will be provided in the clinical study report to justify the exclusion of data. In addition, patients with several missing samples around the expected T_{max} and patients for whom AUC estimation was considered not be reliable due to several missing samples (50% or more of the data are missing) may be excluded from the PK parameter (Cmax and/or AUC) calculation and PK parameter summary.

The following PK parameters will be determined in Parts 1 and 2, and in Chinese patients with the intensive PK schedule in Part 3,, as permitted by data:

- C_{max} .
- t_{max} .
- AUC_{∞} .
- AUC_{last} .
- λ_z .
- $t_{1/2z}$.
- CL.
- V_{ss} .
- Accumulation ratio based on AUC_{last} .

Individual PK parameters will be presented in listings, PK parameters for Cycle 1 Day 1, Cycle 1 Day 15, Cycle 2 Day 1, and Cycle 2 Day 15, as appropriate, will be summarized and grouped by dosing schedule, dose level, and study day by phases (escalation and expansion). The SD and CV

will be reported on at least 3 non-missing values. Except for t_{max} , the summary statistics will consist of: N, mean, SD, CV, geometric mean, geometric CV, median, min, and max. The summary statistics for t_{max} will consist of: N, median, min, and max.

The PK data collected in this study are intended to contribute to future population PK analyses of modakafusp alfa. These population PK analyses may include data collected in other modakafusp alfa clinical studies. The analysis plan for the population PK analysis will be separately defined, and the results of these analyses will not be reported in the clinical study report.

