4.6.3 Changes to Modakafusp Alfa Infusion

The initial administration over 4 hours with premedications and postmedication was based on the administration schema of the only commercialized anti-CD38, daratumumab. Daratumumab is an IgG1 monoclonal antibody with intact antibody-dependent cellular cytotoxicity, antibody-dependent cellular phagocytosis and immune-mediated tumor cell lysis through complement dependent cytotoxicity. Modakafusp alfa belongs to the IgG4 class which does not have immune-effector properties.

Amendment 05 allowed optional administration of premedications and shortened the infusion time of modakafusp alfa to 1 hour. As of Amendment 6, based on the experience with infusion reactions in patients not receiving premedications per the guidance set forth in Amendment 05, it was strongly recommended that all patients receive premedications prior to modakafusp alfa dosing and any decision to stop premedications would have to be discussed with and agreed upon by the sponsor. In addition, patients receiving modakafusp alfa doses ≥6 mg/kg are treated with additional premedication and the dose is delivered over a longer infusion time.

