13.1.4 PK Analysis

PK parameters will be estimated using noncompartmental methods with Phoenix WinNonlin. The PK parameters will be estimated from the concentration-time profiles for the PK population. The following PK parameters will be determined in Parts 1 and 2, and in Chinese patients with the intensive PK schedule in Part 3, as permitted by data:

- C_{max}.
- t_{max}.
- AUC_∞.
- AUC_{last}.
- λ_z .
- $t_{1/2z}$.
- CL.
- V_{ss}.
- Accumulation ratio based on AUC_τ (area under the concentration-time curve during a dosing interval).

PK parameters will be summarized using descriptive statistics. Individual modakafusp alfa concentration-time data and individual PK parameters will be presented in listings and tabulated using summary statistics by dose cohort. Individual and mean concentration-time profiles will be plotted by dose cohort.

The PK data collected in this study are intended to contribute to future population PK analyses of modakafusp alfa. These population PK analyses may include data collected in other modakafusp alfa clinical studies. The analysis plan for the population PK analysis will be separately defined, and the results of these analyses will be reported separately.

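### SAP 7.11.1.2 bases the accumulation ratio on AUClast where the protocol specifies AUCtau, so the ratio is biased whenever the last measurable time differs between the two occasions

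*SAP*

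**What the plan says.** Protocol 13.1.4 lists "Accumulation ratio based on AUC_τ (area under the concentration-time curve during a dosing interval" among the parameters to be derived. The corresponding bullet in SAP 7.11.1.2 reads "Accumulation ratio based on AUC_{last". The other parameters in the two lists agree. AUCtau still appears in the SAP abbreviation list but is not used in 7.11.1.2. Neither the SAP's version 3 to 4 summary of changes nor its change history in 7.14 mentions the substitution.

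For BLQ values after tmax, SAP 7.11.1.2 states that "the concentration-time curve will be considered to have terminated at the time of the last measurable concentration". It also lets the clinical pharmacologist exclude values near the LLOQ.

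On grouping, SAP 7.11.1.1 summarises concentrations "grouped by dosing schedule, dose level, nominal infusion duration, and study day by phases (escalation and expansion"). SAP 7.11.1.2 says that parameters, which include Cmax and tmax, "will be summarized and grouped by dosing schedule, dose level, and study day by phases (escalation and expansion"), without infusion duration. The protocol asks for parameters "tabulated using summary statistics by dose cohort" and does not mention infusion duration either. According to Protocol 4.6.3, Amendment 5 "shortened the infusion time of modakafusp alfa to 1 hour"; before that the infusion was a 4-hour ramp.

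**The concern.** AUCtau covers a fixed interval. AUClast runs to whichever sample was last measurable, and that can differ between cycles in one patient. A ratio of two AUClast values can therefore move away from 1 with no change in drug handling.

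This matters because the ratio is most likely to be read here as a check on loss of exposure. With a half-life under 24 h and dosing intervals of 7 to 28 days, almost no accumulation is possible, so a value below 1 would draw attention. The protocol reports falling concentrations on repeated dosing in monkeys (4.6.1), and SAP 7.11.3 plans to look at the effect of ADA on PK. A shortened sampling window could imitate that effect, or exaggerate a real one.

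The grouping point is smaller. Cmax and tmax depend on infusion length, and both are listed secondary endpoints. If one schedule and dose cell holds patients infused over 4 h and over 1 h, its summary mixes two conditions that the SAP separates for concentrations.

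**Working it through.** The plan gives no numerical accumulation ratio, so there is no figure to reproduce. The check compares the texts and then sizes the effect.

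**Inputs.** The only half-life in the documents is under 24 h (Protocol Appendix J, Czech text). Half-lives of 3, 6, 12 and 24 h are assumptions. Sampling times come from Protocol Appendix C. Schedules C and D have samples at 24, 48 and 168 h after end of infusion. Schedule A has samples at 24 and 72 h after start of infusion on C1D1 and C1D15, but only predose and 4 h on C2D15.

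**1. The ratio on AUCtau with unchanged PK.** Accumulation = 1/(1 − 2^(−tau/h)), where h is the half-life.
- Weekly dosing, tau = 168 h, h = 24 h: 1/(1 − 2^(−7)) = 1.008.
- Q2W and Q4W: 1.00 at every assumed half-life.

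**2. The ratio on AUClast with unchanged PK.** For a mono-exponential decline, AUC(0–t)/AUCinf = 1 − 2^(−t/h). If the last measurable time is 24 h on one occasion and 48 h on the other, the ratio is (1 − 2^(−24/h))/(1 − 2^(−48/h)) = 1/(1 + 2^(−24/h)).

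| Half-life | Calculation | Ratio | Same, with a 1 h infusion modelled |
|---|---|---|---|
| 3 h | 1/(1 + 1/256) | 1.00 | 1.00 |
| 6 h | 1/(1 + 1/16) | 0.94 | 0.94 |
| 12 h | 1/(1 + 1/4) | 0.80 | 0.81 |
| 24 h | 1/(1 + 1/2) | 0.67 | 0.67 |

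If the shift goes the other way, the infusion model gives 1.06, 1.24 and 1.49 at 6, 12 and 24 h. If the last times match, the ratio is 1.00.

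**3. Schedule A, C2D15.** SAP 7.11.1.2 includes this day among those summarised, as appropriate. With a 4 h infusion, AUC(0–4 h) is about 20%, 11% and 6% of AUC(0–72 h) for half-lives of 6, 12 and 24 h. An AUClast ratio of C2D15 to C1D15 would reflect the sampling scheme only. AUCtau would not be well estimated from those two samples either.

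**4. Infusion length.** With zero-order infusion over T hours, Cmax is proportional to (1 − e^(−kT))/(kT), with k = ln 2/h. At h = 3 h, k = 0.231: T = 4 gives 0.653, T = 1 gives 0.893, and the ratio is 0.73. At 6, 12 and 24 h the ratio is 0.85, 0.92 and 0.96. Expected tmax moves from about 1 h to about 4 h. AUCinf is unchanged (ratio 1.00) under linear PK.

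**5. Can a cell be mixed?** Schedules B to D were added at Amendment 4 (22 October 2018) and the infusion was shortened at Amendment 5 (3 July 2019), so it is possible. The documents do not show that any cell actually is. Part 3 is planned at 1 h in both arms, and doses of 6 mg/kg and above have their own rule (Protocol 8.1).

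**The case against.** The strongest reply is that the ratio carries little weight. It is in no endpoint list and no decision uses it. AUCinf and CL are summarised directly by schedule, dose level and study day, and the effect of ADA on PK has its own evaluation. Nominal Day 1 sampling is the same in Cycles 1 and 2, so the bias needs a missed, excluded or BLQ sample. The 48 h example cannot arise in Schedules A or B, which have no 48 h sample. A BLQ value in one cycle only, with unchanged PK, requires a true concentration close to the LLOQ. AUCtau is not free of difficulty: after 28 days the next predose sample is at least 28 half-lives out and very probably BLQ, so AUCtau rests on an extrapolated terminal phase, and the protocol describes nonlinear, target-mediated elimination. All of this stands. It limits how often and how far the ratio misleads. It does not justify an unrecorded change to a less stable definition.

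On infusion duration, the objection that this is no departure from the protocol is correct. For half-lives of 12 to 24 h the modelled Cmax shift is 4% to 8%, small beside the between-subject variability of 30% to over 100% given in Protocol 4.6.2.1. The two effects also peak at opposite ends: a long half-life makes the AUClast bias large and the Cmax shift small, so the worst cases do not occur together.

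**Conclusion.** The mismatch is real and should be corrected. SAP 7.11.1.2 departs from Protocol 13.1.4 without a recorded reason, and the SAP's own rule for ending the curve makes the AUClast ratio depend on sampling. With unchanged PK, a 48 h to 24 h shift in the last measurable time gives about 0.94, 0.80 or 0.67 for half-lives of 6, 12 or 24 h. These figures rest on a mono-exponential decline and assumed half-lives. The LLOQ and the number of patients affected are not given.

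The infusion-duration gap is a secondary inconsistency within the SAP. It lowers Cmax by about 4% to 27% at 4 h against 1 h (half-lives of 24 to 3 h) and shifts tmax. The number of mixed cells is unknown.

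A reader might infer that cycle-to-cycle and dose-level PK comparisons as a whole reflect sampling and infusion length rather than exposure. The documents do not support that. Day 1 sampling matches across Cycles 1 and 2. AUCinf and CL are reported in their own right and, under linear PK, do not depend on infusion length. Nor do the documents say that ADA-driven loss of exposure is expected in patients: the evidence cited is from monkeys. The ORR analysis is not affected.

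**What to change.** - In SAP 7.11.1.2, change the basis of the accumulation ratio from AUClast to AUCtau, as in Protocol 13.1.4, and record the correction in the change table. Name the two occasions being compared, since the protocol names none.
- Where AUCtau is not estimable, use the partial AUC to the same nominal time on both occasions. Where sampling does not support either, as on Schedule A C2D15, report no ratio.
- Add nominal infusion duration to the grouping of the Cmax and tmax summaries, to match 7.11.1.1.

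The cost is a few words in the SAP and a re-run of standard noncompartmental output. A few patients will have a common-interval ratio or none, and some summary cells will become smaller.
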